2.3 RISK/BENEFIT ASSESSMENT

2.3.1 KNOWN POTENTIAL RISKS

IFx-Hu2.0 primes the immune system to a broad array of patient-specific tumor antigens. When breaking tolerance to tumor-associated antigens, which are 'self' antigens, there is a possibility of inducing some form of autoimmunity. Since efficacy and adverse events of immunotherapies are in general mediated by the same underlying pathways and mechanisms, there may be an increased risk of autoimmunity with immunotherapies such as IFx-Hu2.0. Patients receiving immunotherapies have been reported to experience mild pyrexia, cutaneous reactions, diaphoresis, rigor, tachypnea and hypotension.

In the IFx-Hu2.0 monotherapy phase I trial (NCT03655756), eight patients were screened, seven patients were enrolled and treated, and six patients were evaluable for the primary endpoint. There was one screen failure and one death unlikely related to the study drug as determined by the principal investigator. The primary outcome measure of this trial was the rate of DLTs defined as the rate of grade 3 to 5 treatment-related adverse events (AEs) that were deemed unacceptable toxicities by the principal investigator. No grade 3 to 5 treatment-related adverse events (AE) per CTCAE v5.0 were reported (Grade 1 – mild; Grade 2 – moderate). Table 2 and Table 3 reflect all AEs observed in this trial.

Table 2 Treatment-Related AEs based on preliminary data from the IFx-Hu2.0 monotherapy phase I trial (NCT03655756)

All Treatment-Related Adverse Events (Attribution: possible to definite), n=6	Number of Patients (%)	Severity
Injection site reaction	4 (67%)	Mild to Moderate
Tumor hemorrhage	2 (33%)	Mild to Moderate
Tumor pain	1 (17%)	Moderate
Erythema	1 (17%)	Mild
Paresthesia	1 (17%)	Mild
Back pain	1 (17%)	Mild
Lymphocyte count decreased	1 (17%)	Mild
Muscle cramp	1 (17%)	Mild
Pruritus	1 (17%)	Mild
Total	6 (100%)	

Table 3 All AEs based on preliminary data from the IFx-Hu2.0 monotherapy phase I trial (NCT03655756)

All Adverse Events, n=7	Number of Patients (%)	Severity
Injection site reaction	4 (67%)	Mild to Moderate
Tumor hemorrhage	2 (33%)	Mild to Moderate
Hypertension	2 (33%)	Mild to Severe
Erythema	1 (17%)	Mild
Paresthesia	1 (17%)	Mild
Back pain	1 (17%)	Mild
Lymphocyte count decreased	1 (17%)	Mild
Muscle cramp	1 (17%)	Mild
Pruritus	1 (17%)	Mild
Anorexia	1 (17%)	Mild
Dry mouth	1 (17%)	Mild
Insomnia	1 (17%)	Mild
Flatulence	1 (17%)	Mild
Lymphedema	1 (17%)	Mild
Constipation	1 (17%)	Moderate
Tumor pain	1 (17%)	Moderate

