8.2.3.2 RELATIONSHIP TO STUDY INTERVENTION

All adverse events (AEs) must have their relationship to study intervention assessed by the investigator who examines and evaluates the participant based on temporal relationship and his/her clinical judgment. The degree of certainty about causality will be graded using the categories below. In a clinical trial, the study product must always be suspect.

1. **Definitely Related** – There is clear evidence to suggest a causal relationship, and other possible contributing factors can be ruled out. The clinical event, including an abnormal laboratory test result, occurs in a plausible time relationship to study intervention administration and cannot be explained by concurrent disease or other drugs or chemicals. The response to withdrawal of the study intervention (dechallenge) should be clinically plausible. The event must be pharmacologically or phenomenologically definitive., with use of a satisfactory rechallenge procedure if necessary.
2. **Probably Related** – There is evidence to suggest a causal relationship, and the influence of other factors is unlikely. The clinical event, including an abnormal laboratory test result, occurs within a reasonable time after administration of the study intervention, is unlikely to be attributed to concurrent disease or other drugs or chemicals, and follows a clinically reasonable response on withdrawal (dechallenge). Rechallenge information is not required to fulfill this definition.
3. **Potentially Related** – There is some evidence to suggest a causal relationship (e.g., the event occurred within a reasonable time after administration of the trial medication). However, other factors may have contributed to the event (e.g., the participant's clinical condition, other concomitant events). Although an AE may rate only as "possibly related" soon after discovery, it can be flagged as requiring more information and later be upgraded to "probably related" or "definitely related", as appropriate.
4. **Unlikely to be related** – A clinical event, including an abnormal laboratory test result, whose temporal relationship to study intervention administration makes a causal relationship improbable (e.g., the event did not occur within a reasonable time after administration of the study intervention) and in which other drugs or chemicals or underlying disease provides plausible explanations (e.g., the participant's clinical condition, other concomitant treatments).

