8.2.6 SERIOUS ADVERSE EVENT REPORTING

Serious events will be documented on the current OMB approved FDA Form 3500A following the current instructions for reporting. The study clinician will immediately report to the sponsor any serious adverse event, whether or not considered study intervention related, including those listed in the protocol or investigator brochure. The report must include an assessment of whether there is a reasonable possibility that the study intervention caused the event. Study endpoints that are serious adverse events (e.g., all-cause mortality) must be reported in accordance with the protocol unless there is evidence suggesting a causal relationship between the study intervention and the event (e.g., death from anaphylaxis).

All serious adverse events (SAEs) will be followed until satisfactory resolution or until the site investigator deems the event to be chronic or the participant is stable. Other supporting documentation of the event may be requested by the study sponsor and should be provided as soon as possible.

The medical monitor will review all adverse event reports and ensure that participants are receiving appropriate clinical care and identify any potential safety concerns. The medical monitor will assess the information provided to determine the relatedness of the event to the study intervention as well as propose any changes to the protocol and/or consent form based on the event. The study sponsor will be responsible for notifying the Food and Drug Administration (FDA) of any unexpected fatal or life-threatening suspected adverse reaction as soon as possible, but in no case later than 7 calendar days after the sponsor's initial receipt of the information. In addition, the sponsor must notify FDA and all participating investigators in an Investigational New Drug (IND) safety report of potential serious risks, from clinical trials or any other source, as soon as possible, but in no case later than 15 calendar days after the sponsor determines that the information qualifies for reporting.

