9.2 SAMPLE SIZE DETERMINATION

The intent of this study is to enroll approximately 100 evaluable patients to assess the safety of IFx-Hu2.0 as a monotherapy. A sample size of 100 has the following precision for estimation of DLT rates ranging from 0.1 to 0.5. A DLT is defined as an adverse event equal to or greater than grade 3, at least possibly related to the investigational agent, occurring within a 4-week period following IP administration, and deemed as having unacceptable toxicity by the principal investigator and/or medical monitor. Precision is measured by 1-sided 95% upper confidence limit on the estimated DLT rate via exact binomial distribution. For example, if no DLT is observed in patients on IFX-Hu 2.0, then the true underlying DLT rate is lower than 0.099 with 95% confidence.

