9.4.2 SAFETY ANALYSES

Maximum planned sample size	100
The event probability (ϑ)	0.2
Desired probability of early stopping	0.05

The trial will be stopped if the number of Dose Limiting Toxicities (DLTs) is equal to or exceeds b_n out of n patients with completed follow-up.

Number of Patients, n	1	2	3	4	5	6	7	8	9	10	11	12	13	14	15	16	17	18	19	20
Boundary, b_n	-	-	3	4	4	5	5	6	6	6	7	7	7	8	8	8	9	9	9	10
Number of Patients, n	21	22	23	24	25	26	27	28	29	30	31	32	33	34	35	36	37	38	39	40
Boundary, b_n	10	10	11	11	11	11	12	12	12	13	13	13	13	14	14	14	15	15	15	15
Number of Patients, n	41	42	43	44	45	46	47	48	49	50	51	52	53	54	55	56	57	58	59	60
Boundary, b_n	16	16	16	17	17	17	17	18	18	18	18	19	19	19	20	20	20	20	21	21
Number of Patients, n	61	62	63	64	65	66	67	68	69	70	71	72	73	74	75	76	77	78	79	80
Boundary, b_n	21	21	22	22	22	22	23	23	23	23	24	24	24	24	25	25	25	25	26	26
Number of Patients, n	81	82	83	84	85	86	87	88	89	90	91	92	93	94	95	96	97	98	99	100
Boundary, b_n	26	26	27	27	27	27	28	28	28	28	29	29	29	29	30	30	30	30	31	31

This boundary is equivalent to testing the null hypothesis, after each patient, that the event rate is equal to 0.2, using a one-sided level 0.008340 test.

Sequential boundaries will be used to monitor dose-limiting toxicity rate. The accrual will be halted if excessive numbers of DLTs are seen, that is, if the number of DLTs is equal to or exceeds b_n out of n patients with full follow-up. This is a Pocock-type stopping boundary that yields the probability of crossing the boundary at most [probability of early stopping] when the rate of DLTs is equal to the acceptable rate [event probability θ] (16).

θ	ϕ^*	$E[Y]$	$SD[Y]$	$E[N]$	$SD[N]$	$E[Y/N]$	$SD[Y/N]$
0.20	0.0497	19.31	4.40	96.58	16.21	0.21	0.10
0.30	0.6116	20.12	7.86	67.08	34.29	0.37	0.16
0.40	0.9883	11.85	6.31	29.65	22.10	0.50	0.18
0.50	1.0000	7.61	3.56	15.22	10.91	0.61	0.19
0.60	1.0000	5.71	2.31	9.52	6.29	0.71	0.19
0.70	1.0000	4.62	1.63	6.60	3.96	0.79	0.17
0.80	1.0000	3.89	1.14	4.86	2.51	0.87	0.14
0.90	1.0000	3.37	0.69	3.74	1.41	0.94	0.11
1.00	1.0000	3.00	0.00	3.00	0.00	1.00	0.00

Definitions:

Y = the number of events, random, between 0 and N

N = the number of patients, random, between 1 and K

ϕ^* = the actual probability of early stopping (hitting the boundary)

$E[]$ denotes the expected value (mean)

$SD[]$ denotes the standard deviation

Resource: <http://cancer.unc.edu/biostatistics/program/ivanova/ContinuosMonitoringForToxicity.aspx>

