3.7. Key Data Items

Study Analysis Population Definition:

- Safety analysis set: All enrolled patients who have received at least 1 dose of IFx-Hu2.0.

Important Derived Variables:

- Age = (Screening Date – Date of Birth +1)/365.25.
- Prior Medications and Treatments: the medications and treatments started before enrolled to the study.
- Concomitant Medication and Treatments: the medications and treatments started after being enrolled to the study.
- Baseline: Day 0 (Baseline Visit). All clinical measurements collected at Day 0 or before the dose of IFx-Hu2.0 on Day 0 will be analyzed as baseline.
- Post Baseline (post dose): All clinical measurements collected after the dose of IFx-Hu2.0 on Day 0 will be analyzed as post baseline.
- Dose-Limiting Toxicity (DLT): Treatment emergent adverse event (TEAE) equal to or greater than grade 3, at least possibly related to the investigational agent, occurring within a 4-week period following IFx-Hu2.0 administration

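### One or two treatment-related deaths never oblige a pause in dosing: the only compulsory halt in the available text, b_n, is never below 3, and suspension during review is discretionary

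*Protocol*

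**What the plan says.** **The halt rule.** Protocol 9.4.2 gives a Pocock-type boundary against a DLT rate of 0.2. Its wording is compulsory: "The accrual will be halted if excessive numbers of DLTs are seen, that is, if the number of DLTs is equal to or exceeds b_n". The count that matters is one that "is equal to or exceeds b_n out of n patients with full follow-up". The printed table has no value at n = 1 and 2, then 3 at n = 3, 4 at n = 4, 6 at n = 10, 10 at n = 20, 18 at n = 50 and 31 at n = 100.

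**What counts as a DLT.** Protocol 9.2 counts an event of grade 3 or higher, at least possibly related, within 4 weeks of dosing, "and deemed as having unacceptable toxicity by the principal investigator and/or medical monitor". Grade 5 carries no extra weight.

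**What a related death sets in motion.**
- 8.2.6: "The study clinician will immediately report to the sponsor any serious adverse event, whether or not considered study intervention related". The medical monitor reviews every report. The FDA is told within 7 calendar days if the reaction is fatal or life-threatening, unexpected and suspected, and within 15 days for other potential serious risks.
- 10.1.6: the medical monitor reviews safety on an ongoing basis and may, among other outcomes, table the matter.
- 10.1.2: the study may be suspended on an open list of grounds, the first of which is risk to participants.
- End of 9.4.2: after a halt, the medical monitor makes a recommendation and the sponsor informs the FDA. In context this follows a crossing of b_n and is not a separate trigger.

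**Who decides relatedness.** Two parties do. Section 8.2.3.2 says "All adverse events (AEs) must have their relationship to study intervention assessed by the investigator who examines and evaluates the participant"; 8.2.6 says "The medical monitor will assess the information provided to determine the relatedness of the event to the study intervention".

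The SAP plans no interim analysis (3.6) and adds no halt rule.

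**The concern.** A boundary on a 20% DLT rate is a rate monitor. It is not built to react to a single fatal event, so a protocol normally pairs it with a rule for deaths. Here the pairing consists of reporting, review and a power to suspend. The step that obliges sites to stop dosing while the case is examined is missing.

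Three features make this matter somewhat more:
- About five sites dose in parallel (5.5), and one site may not know of a death at another unless told.
- The patients have early-stage disease (2.1) for which primary treatment is surgical (2.2), so holding a new injection for some days costs them little.
- Human safety data are thin. In the one trial described in 2.3.1, seven patients were treated and no related grade 3 to 5 event was reported, but "There was one screen failure and one death unlikely related to the study drug as determined by the principal investigator". Attribution decided how that death was counted. It would also decide whether any pause operates here, so a pause rule has to say whose judgement counts.

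At stake are the patients not yet dosed when a related death occurs. A pause does nothing for those already injected.

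**Working it through.** **1. Reproduce the boundary.** Inputs from 9.4.2: null rate 0.2, one-sided level 0.008340, n up to 100. For each n, b_n is the smallest r with P(X ≥ r | n, 0.2) ≤ 0.008340.
- n = 1: P(X ≥ 1) = 0.20, above the level, so no boundary.
- n = 2: P(X ≥ 2) = 0.2² = 0.04, above the level, so no boundary.
- n = 3: P(X ≥ 3) = 0.2³ = 0.008, so b_3 = 3.
- n = 4: P(X ≥ 3) = 4 × 0.008 × 0.8 + 0.0016 = 0.0272, too large; P(X ≥ 4) = 0.0016, so b_4 = 4.

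All 100 printed entries match. An exact forward recursion over the printed boundary gives these probabilities of early stopping:

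| DLT rate | Recomputed | Printed |
|---|---|---|
| 0.20 | 0.0490 | 0.0497 |
| 0.30 | 0.6137 | 0.6116 |
| 0.40 | 0.9878 | 0.9883 |

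The small gaps look like simulation error in the printed table. The boundary is sound for its purpose.

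**2. Can deaths alone cross it?** The minimum of b_n is 3, so one or two DLTs cannot cross at any n, even if they are the first two patients. Three cross only at n = 3, because b_n is at least 4 from n = 4. After two related deaths, the further DLTs needed are:
- n = 10: 6 − 2 = 4
- n = 20: 10 − 2 = 8
- n = 50: 18 − 2 = 16
- n = 100: 31 − 2 = 29

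If related deaths were the only DLTs, at assumed rates of 1%, 2% and 5%, the same recursion gives a probability of ever crossing of 0.000001, 0.0000085 and 0.00015. This restates that a boundary for a 20% rate does not detect a rate of a few per cent.

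**3. How many patients does a pause protect?** Section 5.5 gives about 100 patients in up to 12 months. Patients dosed during a review of d days = (100 / 365) × d:
- 7 days: 1.92
- 15 days: 4.11

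The 7 and 15 days are FDA reporting deadlines, used only as a scale for review time. If recruitment took 6 months (an assumption), the figures double to 3.84 and 8.22.

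The documents give no fatal rate. Expected further related deaths among newly dosed patients = patients × assumed rate:

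| Assumed rate | 7 days | 15 days |
|---|---|---|
| 1% | 0.019 | 0.041 |
| 2% | 0.038 | 0.082 |
| 5% | 0.096 | 0.205 |

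These also double with 6-month recruitment.

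**4. How often would a death-triggered pause operate?** With q the assumed chance per patient of a death that either assessor calls at least possibly related, P(at least one pause in 100 patients) = 1 − (1 − q)^100. This is 9.5% at q = 0.1%, 39% at 0.5%, 63% at 1% and 87% at 2%.

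**The case against.** The best defence is that b_n was never meant to handle single deaths, and that the protocol handles them elsewhere. A related death is reported at once, reviewed by the medical monitor and, if unexpected, notified to the FDA within 7 days. The study can be suspended for unacceptable risk, and 10.1.2 lets it resume only when concerns are addressed to the satisfaction of the sponsor, IRB and/or FDA. What is missing is automaticity. That is correct. A reader might infer that nobody could stop the trial after a death, or that a stated rule is broken; the documents support neither.

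A second objection is that the proposed pause has no fixed length and ends on a decision by the same parties who can suspend now, so deaths avoided over 7 or 15 days cannot be credited to it. This also stands: the figures in step 3 show scale and are not a promised gain. What survives is that review would come before the next injection instead of alongside it.

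Three further inferences should be avoided:
- *Total human exposure is seven patients.* The text describes one trial, labels its data preliminary, and part of the account of earlier human use is not in the available text.
- *The SAP drops the unacceptable-toxicity judgement.* SAP 3.7 stops at "at least possibly related to the investigational agent, occurring within a 4-week period following IFx-Hu2.0 administration", but SAP 2.3 includes the clause. The SAP is inconsistent with itself, which does not bear on this point.
- *The boundary is wrong.* It reproduces in full.

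**Conclusion.** The point holds as a gap between may and must. In the available text, no number of related deaths below three obliges a halt, and three do so only as the first three patients with full follow-up. Every other safeguard requires reporting or review, or permits suspension. None requires dosing to wait.

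The size is modest: about 2 further patients dosed per 7 days at planned accrual, and no gain at all if the sponsor or sites would pause anyway. The fatal rates in the working are assumptions, and the benefit depends on how long review takes.

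One limit applies to the word *only*. Some pages were not available: protocol front matter, part of the prior-human-experience text in 2.2, part of 2.3.1, the place where 10.1.5 (key roles and governance) belongs, and SAP front and end pages. A halt rule there is unlikely from their position but cannot be excluded.

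Because the harm is irreversible and the remedy costs little, the change is worth making as a cheap improvement.

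**What to change.** Leave b_n unchanged. Add to protocol 9.4.2 and 10.1.6:

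> Any death within 4 weeks of IFx-Hu2.0, or within the SAE reporting period in 8.2.4, that the investigator or the medical monitor judges at least possibly related pauses new dosing at all sites, whatever b_n is and without waiting for full follow-up or the unacceptable-toxicity judgement, until the medical monitor has completed a documented review and the sponsor has recorded the decision to resume or stop and informed the FDA.

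If the two assessors disagree, the related call triggers the pause. Patients already dosed keep their Day 28 visit and excision. State that this is a review pause and not a crossing of b_n, so the printed operating characteristics of b_n still apply.

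Cost: a sentence or two in an amendment, using the existing medical monitor, SAE reports and temporary-halt notice. The downside is a possible short accrual pause for a death later judged unrelated.

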4.3 END OF STUDY DEFINITION

A participant is considered to have completed the study if he or she has completed all phases of the study including the last visit or the last scheduled procedure shown in the Schedule of Activities (SoA), Section 1.3. The end of the study is defined as completion of the last visit or procedure shown in the SoA in the trial globally.

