5.5 STRATEGIES FOR RECRUITMENT AND RETENTION

This study will have a goal of 100 evaluable patients. It is the intent of the study team to recruit additional patients to be screened and enrolled if any of the existing patients are lost to follow-up or withdraw consent.

Potential participants will be identified by sites through physician referrals, available recruitment databases, and other methods available to participating sites to identify potential participants. Specific recruitment materials may be developed by the sponsor. In addition, if any site decides to utilize participant-focused materials for recruitment, such materials and a usage plan will be submitted for IRB review and approval prior to implementation. A clinical enrollment manager (CEM) or sponsor designee(s) may locally support the research team and facilitate patient recruitment at the study site in addition to all other measures/efforts. Under no circumstance will referral fees, incentives, or bonuses to physicians for recruitment be allowed.

There is no specific plan to target participants based on race, gender, or age. All eligible potential participants will be approached for inclusion.

It is anticipated that recruitment will take up to 12 months to complete at approximately five research sites. Sites will be NCI-designated cancer centers, academic medical centers, clinics, and doctor's offices within the United States. Sites can include community facilities as a primary site or a satellite site of a participating center as long as they meet the requirements regarding the proper handling and administration of the investigational agent.

Due to the size and short duration of the study, there is no planned retention or compensation plan for participants. Throughout the study, participants will be reminded about upcoming visits and the procedures to be performed at the visit. New information that surfaces during the study will be communicated to participants through IRB-approved mechanisms.

In alignment with the Internal Revenue Service (IRS) 2020 Standard Mileage Rate (Notice 2020-05), participants can be reimbursed at a rate of 17 cents per mile driven in an automobile for traveling for study-related medical purposes. This will be done approximately one month after travel receipts are submitted by study staff to the sponsor.

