6. Tumor lesion measurement (longest diameter)
7. Urine pregnancy tests for females of reproductive potential; done within 24 hours prior to IFx-Hu2.0 administration, and results must be available prior to IFx-Hu2.0 administration

8. 40 mL of blood for exploratory analysis
9. IFx-Hu2.0 administration

Final Visit (Day 28 ± 5 days) or Early Termination Visit

1. Concomitant medications
2. ECOG performance status
3. Physical exam, including vital signs, weight
4. Electrocardiogram (ECG)
5. Laboratory tests
 - 5.1. Hematology: CBC - hemoglobin, hematocrit, white blood cells (WBC) with differential count, platelet count; blood clotting tests: prothrombin time (PT) and activated partial thromboplastin time (aPTT)
 - 5.2. Biochemistry: CMP - glucose, calcium, albumin, total protein, sodium, potassium, CO2, chloride, BUN, creatinine, total bilirubin, alanine aminotransferase (ALT), aspartate aminotransferase (AST), alkaline phosphatase (ALP), lactate dehydrogenase (LDH), Thyroid tests (TSH and FT4)
 - 5.3. Urinalysis: UA with microscopic evaluation
 - 5.4. Anti-double-stranded DNA (anti-dsDNA) antibody test
 - 5.5. Anti-DNase B Titer, Serum
6. Adverse event recording per CTCAE v5.0
7. Tumor lesion measurement (longest diameter)
8. Serum pregnancy tests for females of reproductive potential
9. 40 mL of blood for immune response evaluation
10. Tumor excision (wide local excision) for pathological response (final)

Unscheduled Visit

If participants require a visit between the baseline and final study visits, then the following procedures may be performed, as indicated (per investigator discretion):

1. Concomitant medications
2. ECOG performance status
3. Physical exam, including vital signs, weight
4. Electrocardiogram (ECG)
5. Laboratory tests
 - 5.1. Hematology: CBC - hemoglobin, hematocrit, white blood cells (WBC) with differential count, platelet count; blood clotting tests: prothrombin time (PT) and activated partial thromboplastin time (aPTT)
 - 5.2. Biochemistry: CMP - glucose, calcium, albumin, total protein, sodium, potassium, CO2, chloride, BUN, creatinine, total bilirubin, alanine aminotransferase (ALT), aspartate aminotransferase (AST), alkaline phosphatase (ALP), lactate dehydrogenase (LDH), Thyroid tests (TSH and FT4)
 - 5.3. Urinalysis: UA with microscopic evaluation
 - 5.4. Anti-double-stranded DNA (anti-dsDNA) antibody test
 - 5.5. Anti-DNase B Titer, Serum
6. Adverse event recording per CTCAE v5.0

7. Tumor lesion measurement (longest diameter)

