7.2 PARTICIPANT DISCONTINUATION/WITHDRAWAL FROM THE STUDY

Participants are free to withdraw from participation in the study at any time upon request.

An investigator may discontinue or withdraw a participant from the study for the following reasons:

1. Pregnancy

2. Significant study intervention non-compliance
3. If any clinical adverse event (AE), laboratory abnormality, or other medical condition or situation occurs such that continued participation in the study would not be in the best interest of the participant
4. Disease progression
5. If the participant meets an exclusion criterion or fails to meet an inclusion criteria (either newly developed or not previously recognized) that precludes further study participation

The reason for participant discontinuation or withdrawal from the study will be recorded on the case report form (CRF). Subjects who sign the informed consent form but do not receive the study intervention may be replaced. Subjects who sign the informed consent form, and receive the study intervention, and subsequently withdraw, or are withdrawn or discontinued from the study will be replaced.

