8 STUDY ASSESSMENTS AND PROCEDURES

8.1 SAFETY AND OTHER ASSESSMENTS

This study will comply with all applicable regulations on IND safety reporting requirements to the FDA in accordance with 21 CFR 312.32. This study will utilize CTCAE v5.0 for toxicity and AE reporting. All appropriate treatment areas at the clinical sites will have access to a copy of the CTCAE v5.0. Careful evaluation to determine the toxicity IFx-Hu2.0 as a monotherapy will be performed. Adverse events will be documented beginning at initiation of treatment (Day 0) as well as at the follow-up visit whether that be end of study as planned or early termination.

Subjects with treatment-related toxicity will be followed for the ongoing drug-related adverse events until resolved, return to baseline, deemed irreversible by the treating physician, the subject has been properly referred to an appropriately licensed practitioner for further evaluation and treatment, or until the subject is lost to follow up, withdrawal of study consent, removal of the subject from the trial by the treating physician, or start of a subsequent anti-cancer therapy.

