8.2.5 ADVERSE EVENT REPORTING

Adverse events will be documented. The principal investigator at the site is responsible for notifying the sponsor of any adverse event as soon as possible. The medical monitor will review all adverse event reports and ensure that participants are receiving appropriate clinical care and identify any potential safety concerns. The medical monitor will assess the information provided to determine the relatedness of the event to the study intervention as well as propose any changes to the protocol and/or consent form based on the event. All adverse events will be documented and reported to the FDA in the annual report. Adverse events that meet the requirements for reporting to the IRB will be reported within the guidelines required by the IRB of record, along with necessary supporting information and revised trial documentation, as necessary.

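### Does a DLT in a treated patient who leaves early and is replaced drop out of the stopping-rule count?

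*Protocol*

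**What the plan says.** Protocol 9.4.2 tabulates a boundary b_n for n = 1 to 100 and halts accrual "if the number of DLTs is equal to or exceeds b_n out of n patients with full follow-up". An earlier sentence in the same section speaks of completed follow-up instead. Neither term is defined. The nearest definition is in section 4.3: "A participant is considered to have completed the study if he or she has completed all phases of the study including the last visit". That sentence goes on to accept, as an alternative, the last procedure in the Schedule of Activities.

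Section 7.2 lists among the reasons for withdrawal: "If any clinical adverse event (AE), laboratory abnormality, or other medical condition or situation occurs such that continued participation in the study" is no longer in the patient's interest. It then says that patients who consent "and receive the study intervention, and subsequently withdraw, or are withdrawn or discontinued from the study will be replaced". Section 5.5 aims for 100 evaluable patients and plans to "recruit additional patients to be screened and enrolled if any of the existing patients are lost to follow-up or withdraw consent".

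Other text bears on the point:

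- Section 9.2 defines a DLT by a four-week window after injection.
- Section 8.1 records adverse events "at the follow-up visit whether that be end of study as planned or early termination".
- Section 6.1.3 gives one procedure list for the "Final Visit (Day 28 ± 5 days) or Early Termination Visit".
- The Schedule of Activities (1.3) marks every Week 4 assessment in its Early Termination column as well.
- SAP 2.1 puts all safety analyses on the set of patients who received at least one dose.

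**The concern.** The patients most likely to raise the question are those the rule is meant to detect. Someone with a DLT may be withdrawn because of it, miss the Week 4 visit and be replaced. If full follow-up means attending Week 4, both the patient and the DLT leave the count, and a DLT-free replacement may come in. The table stops at n = 100, which could suggest that leavers and replacements are not both meant to be counted.

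This is the trial's only numerical stopping rule. If DLT patients were lost more often than others and left out, the trial would stop less often than 9.4.2 prints. Two people applying the rule could also classify the same patient differently. The SAP does not help directly: it does not restate the rule, and its section 3.6 plans no interim analysis.

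**Working it through.** **Reproducing the plan's figures.** Inputs from 9.4.2: acceptable rate 0.2, one-sided level 0.008340, maximum 100 patients. Taking b_n as the smallest k with P(X ≥ k | n, 0.2) ≤ 0.008340 gives all 100 printed values. An exact recursion over the DLT count after each patient, absorbing at b_n, gives stopping probabilities of 0.0490, 0.6137 and 0.9878 at true rates 0.20, 0.30 and 0.40. The protocol prints 0.0497, 0.6116 and 0.9883.

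**Leaving DLT patients out.** Let p be the true DLT rate, w the share of DLT patients who leave uncounted, and r the same share among DLT-free patients. The documents give neither w nor r, so both are assumptions. The DLT rate among counted patients is

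p_c = p(1 − w) / [p(1 − w) + (1 − p)(1 − r)].

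For p = 0.30, w = 10%, r = 0: 0.27 / (0.27 + 0.70) = 0.278. Putting p_c through the recursion:

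| w (r = 0) | p = 0.25 | p = 0.30 | p = 0.40 |
|---|---|---|---|
| 0 | 0.239 | 0.614 | 0.988 |
| 5% | 0.185 | 0.530 | 0.978 |
| 10% | 0.139 | 0.443 | 0.961 |
| 25% | 0.049 | 0.200 | 0.829 |

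At p = 0.30, w = 5% leaves out about 1 DLT of 22 on average, and w = 10% about 2 of 24. With w = 10% and r = 5% the result is 0.526. With w = r the factors cancel, p_c = p, and the result stays at 0.614.

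**Counting every DLT.** If every DLT patient counts in both the DLT number and n, and no DLT-free patient is lost, the printed properties hold for any w. If DLT-free leavers stay out of n, then at p = 0.20:

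- r = 2%: p_c = 0.20 / (0.20 + 0.784) = 0.203, stopping probability 0.055.
- r = 5%: p_c = 0.20 / (0.20 + 0.76) = 0.208, stopping probability 0.066.

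Both exceed the 0.05 cap in 9.4.2. If DLTs entered on the day of onset while DLT-free patients waited four weeks, a simulation of 100,000 runs gives 0.116 at p = 0.20. It assumes even accrual of 100 patients over 365 days and onset uniform over 28 days.

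**Going past n = 100.** The same test gives b_n = 31 at n = 101–102 and 32 at n = 103–106. Run to n = 105, the stopping probability at 0.20 is 0.0499. The end of the table is no reason to discard leavers.

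**The case for a change.** The strongest case for a change is that a pre-specified boundary should leave no doubt about who is counted, and this one does. No sentence says that an early termination visit gives full follow-up. SAP 2.1 is a general statement in a document that does not contain the stopping rule. Toxicity follow-up can end when consent is withdrawn. Discretionary review does not replace a rule whose error rates are printed. A few sentences would settle it.

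The first part stands: the term is undefined, and the supporting text is persuasive rather than conclusive. The arithmetic also stands, and the loss would be serious if one DLT patient in four were left out.

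That outcome needs several things together. DLT patients must leave more often than others, although dosing is one injection, no later dose remains to be stopped, and the one remaining visit is the one at which the tumor is excised. Their early termination visit must be treated as no follow-up. The team must then choose to discard an event already recorded. Nothing in the documents suggests the excess loss, and nothing tells the team to discard the event.

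Nor is a written rule free of consequences. As computed above, counting all DLTs while omitting lost DLT-free patients goes over the 0.05 cap, and wording silent on when a DLT patient enters n could be taken as the day-of-onset version.

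**Conclusion.** No change to the plan follows. The sensible reading of 9.4.2 is that the follow-up condition keeps DLT-free patients from entering n before their four weeks are known. It does not erase a DLT already seen. The DLT window in 9.2, the dosed-patient set in SAP 2.1 and the Early Termination column all point that way, and the replacement provisions in 5.5 and 7.2 concern recruitment only. On that reading, with no loss of DLT-free patients, the printed operating characteristics hold.

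The opposite reading costs about 0.08 to 0.17 in stopping probability at a true rate of 0.30 (0.614 to 0.530 or 0.443), and under 0.03 at 0.40. Those figures assume 5–10% uncounted loss among DLT patients and none among the rest; the cost is zero if the two groups leave equally often. A DLT outside the formal count would still be seen: "The medical monitor will review all adverse event reports", section 10.1.2 allows suspension for unacceptable risk, and SAP 3.2.1 reports the DLT rate on all dosed patients.

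The conclusion rests on the team counting known DLTs in both the DLT number and n. It would weaken only if DLT patients in fact left disproportionately and were left out.
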